8. Statistical considerations.....	13
8.1 Details of statistical analysis	13
8.2 Sample size	13
9. Assessment of safety.....	13
9.1 Serious Adverse Events (SAEs) Definitions.....	13
9.2 Anticipated Adverse Device Effects.....	14
9.3 Reporting of SAE.....	14
9.4 Follow-up of SAE.....	14
10. Ethics and regulatory considerations.....	14
11. Informed consent process.....	14
12. Confidentiality.....	15
13. Data management.....	15
13.1 Data collection.....	15
13.2 Study documentation and record keeping.....	15
13.3 Database management and structure.....	15
14. Procedure of handling withdrawal.....	16

15. Risk of procedure.....	16
16. Study Funding.....	16
17. Publication Policy.....	16
17.1 Authorship Selection.....	16
17.2 Review and Communication Guidelines.....	17
18. References.....	18
19. Appendix.....	19
Signature Page Principal Investigator.....	20

[figure not shown]
List of abbreviations

AF	Atrial Fibrillation
CT	Computed Tomography
ECG	Electrocardiogram
ICE	Intracardiac echocardiogram
IRB	Institutional Review Board
LAAO	Left Atrial Appendage Occlusion
mRS	Modified Rankin Scale
MRI	Magnetic Resonance Imaging
NICL	Non-invasive Cardiac Laboratory
OAC	Oral anti-coagulants
REB	Research Ethics Board
SHC	Sarawak Heart Centre
TIA	Transient Ischemic Attack
TOE	Transesophageal Echocardiogram
TTE	Transthoracic Echocardiogram

Protocol Summary

Full Title	Left Atrial Appendage Occlusion with The Amplatzer™ Amulet™ Device: The Southeast Asia Prospective Observational Study	
Short Title	SEA Amulet™ Study	
Principal Investigator	[name] [name]	
Sponsor	Sarawak Heart Centre	
Funder	St. Jude Abbott Medical	
Primary Objective	To explore on the short-term and long-term (1 year) safety and efficacy of LAA occlusion with the Amplatzer™ Amulet™ Device in the Southeast Asia population on a real-world basis.	
Secondary Objectives	To compare the practice of LAA occlusion with Amplatzer™ Amulet™ Device in Southeast Asia population with the European registries.	
Exploratory Objectives	Cost effectiveness of LAA occlusion with the Amplatzer™ Amulet™ Device in the Southeast Asia.	
Study Population	All-comer study for patients indicated for LAA occlusion with Amplatzer™ Amulet™ Device according to the international guidelines	
Study Design	Multicenter, observational study	
Sample Size	100 patients	
Accrual Period	12 months recruitment + 1-year follow-up.	
Study Duration	Start Date: 1 October 2022	End Date: 1 October 2024

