Assessments	
Subjects will be followed through 1 year post implant.
 
Required Testing
 
• Baseline evaluation: Informed consent, history and physical, 12-lead electrocardiogram (ECG), CHA2DS2-VASc score, HAS-BLED score, Modified Rankin Scale (mRS), medication assessment. Pre-procedural Imaging planning with TOE or CT scan• Procedure: TOE or ICE only when combined with baseline/pre-procedural imaging, and adverse event assessment• Post procedure/Pre-discharge: TTE, medication assessment, adverse event assessment• 1M to 3M: TOE or CT scan, medication assessment, adverse event assessment• 6M (+/- 2 weeks): TOE or CT scan, medication and AE assessment• 12 (+/- 6 weeks): Medication and adverse event assessment• Interim/unscheduled visits: per physician discretion

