3. ELIGIBILITY CRITERIA

This is an all-comer observational study and therefore all patients indicated for LAAO with the Amplatzer™ Amulet™ are eligible for the study. Subjects who meet criteria for eligibility will be asked to participate. Since this observational study is both retrospective and prospective, subjects who had their occluder implanted, been recently implanted or intended to undergo the procedure may be considered to participate in the study. Informed consent will be obtained for data collection purposes.

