4. STUDY DESIGN

4.1 Study Description

This is a both prospective and retrospective, multicenter observational study for all patient indicated for LAAO with the Amplatzer™ Amulet™ device.

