8.2 Sample size

A sample size of 100 patients for the study. This is based on the estimated number of recruitments from the participating centers.

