19. APPENDIX

Appendix A: Schedule of Events

Evaluation	Baseline	LAAO implant	Pre-discharge	1-3mo	6mo	12mo
Informed consent (For prospective data collection only)	X					
CRF form	X					
Demographics	X					
Indication	X					
Clinical examination and investigations	X		X	X	X	X
mRS, CHA2DS2-VASc, HASBLED	X					
Medications	X		X	X	X	X
CT Scan, TOE or ICE	X	X		X	X	
Procedural detail		X				
Safety Outcomes		X	X	X	X	X
Efficacy Outcomes		X	X	X	X	X

Signature Page Principal Investigator

Study title: Left Atrial Appendage Occlusion with The Amplatzer™ Amulet™ Device: The Southeast Asia Observational Study

Short title: Amulet-SEA-01

Version no: 1.2

Version date: 27 October 2022

I have read this protocol and/or amendment and appendices and agree to adhere to the requirements. I will provide copies of this protocol and all pertinent information to the study personnel under my supervision. I will discuss this material with them and ensure they are fully informed regarding the investigational product and the conduct of the study.

I will conduct the study in accordance with the protocol and local regulations.

[name] [name]

Pusat Jantung Hospital Umum Sarawak,
[name],
[name]
[name]
Sarawak, Malaysia

[name]
[name]
MBBS (IMU), MRCP (UK)
CONSULTANT CARDIOLOGIST
SARAWAK HEART CENTRE
[name]

Signature Principal Investigator at the Site

27-Oct-2022

Date

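### The full title says prospective, but Section 3 also admits past implants with no look-back date, consecutive-entry rule or limit, so past cases can enter selectively and be followed up incompletely

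*Protocol*

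**What the plan says.** The full title in the Protocol Summary reads "The Southeast Asia Prospective Observational Study". The signature page after Appendix A gives it as "The Southeast Asia Observational Study", without the word. Section 4.1 states the design: "This is a both prospective and retrospective, multicenter observational study for all patient indicated for LAAO". Section 16 likewise says the grant supports both retrospective and prospective data collection.

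Section 3 opens with an all-comer statement: "This is an all-comer observational study and therefore all patients indicated for LAAO with the Amplatzer™ Amulet™ are eligible for the study". It continues: "Subjects who meet criteria for eligibility will be asked to participate". It then extends entry to past cases: "subjects who had their occluder implanted, been recently implanted or intended to undergo the procedure may be considered to participate in the study". Patients already implanted are listed separately from those recently implanted, and neither group is given a date limit.

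The size is 100, and Section 8.2 explains: "This is based on the estimated number of recruitments from the participating centers". It gives no split between past and new implants.

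Under Assessments, the Protocol Summary requires TOE or CT at 1 to 3 months and again at 6 months: "6M (+/- 2 weeks): TOE or CT scan, medication and AE assessment". Section 4.2 lists leak and device-related thrombus among the primary outcomes, together with mortality, pericardial effusion and access site complications.

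Three other provisions bear on past cases:

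- Section 3.1 requires that the patient can and will come back for follow-up visits.
- Section 9 starts adverse event assessment at the signing of consent.
- On consent, Section 3 refers to data collection without restriction, while Section 11 and the first row of Appendix A refer to prospective data only.

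**The concern.** A past implant differs from a new one because its outcome may already be known when someone decides whether to enter it. Three safeguards normally deal with this: a look-back date fixed in advance, an obligation to list every case from that date, and a rule counting events from the procedure whatever the date of consent. The Protocol states none of the first two and, for adverse events, states the opposite of the third.

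The primary objective is to describe safety and efficacy to one year, and the secondary objective is a comparison with European registries. With a fixed target of 100 and an unbounded pool of past cases, the mix of implant years and outcomes depends on which cases each centre puts forward. Primary outcomes that need a scan, or that occur around the procedure, may also be captured differently in past and new cases. A report under a prospective title would give readers no warning of this.

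**Working it through.** **No sample-size figure to reproduce.** The 100 is a recruitment estimate with no formula behind it. The check compares provisions and uses simple counts.

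**1. Title against design.** The Summary title says prospective. Sections 3, 4.1 and 16 say both retrospective and prospective, and the signature-page title omits the word. The body is consistent with itself, so the full title is the outlier.

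**2. Limit on past cases.** Largest permitted number of past cases = 100 − required minimum of prospective patients. No minimum is stated, so 100 − 0 = 100. This is an upper bound on what the text allows and says nothing about the expected mix.

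**3. Imaging windows (Protocol Summary, Assessments).**

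- The first window closes 3 months after implant.
- The second closes at 6 months + 14 days = 6 + 14/30.44 = 6.46, or about 6.5 months.
- Implanted less than 1 month before entry: neither window missed.
- Implanted more than 3 months before entry: first window passed.
- Implanted more than about 6.5 months before entry: both windows passed.

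For the last two groups, imaging that the study can no longer schedule in window exists only if it was done in routine care.

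**4. Survivor effect of the return-visit criterion (illustration).** A patient who must be able to return is alive at entry. One who enters after completing a year from implant cannot contribute a one-year death. Let f be the share of the 100 entered that late and m the true one-year mortality. The Protocol gives neither, so both are assumptions shown over a range.

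Expected observable deaths = 100 × (1 − f) × m

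| f | m = 5% | m = 10% | m = 15% |
|---|---|---|---|
| 0 | 5 | 10 | 15 |
| 25% | 3.75 | 7.5 | 11.25 |
| 50% | 2.5 | 5 | 7.5 |
| 100% | 0 | 0 | 0 |

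Divided by 100 patients, observed mortality is (1 − f) × m, so the proportional shortfall equals f.

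**5. Peri-procedural events.** If assessment starts at consent and consent follows the implant, everything between the two dates falls outside the assessed period. Pericardial effusion and access site complications are the primary outcomes most exposed. If a retrospective patient gives no consent, as Section 11 and Appendix A allow, the Section 9 start date is undefined.

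**6. Sensitivity to one omitted case.** Section 1 quotes 1.3% for stroke or TIA (LAARGE) and 1.6% for device-related thrombus (the Amulet observational study). At those rates, 100 × 0.013 = 1.3 and 100 × 0.016 = 1.6 events are expected. One omitted event changes a rate by about 1/100 = 1 percentage point, close to the size of the rates themselves.

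**The case against.** A reader might infer that the cohort will be hand-picked, or made up entirely of old cases. The documents do not support either reading. Section 3 declares an all-comer study and says eligible subjects will be asked to take part. In that setting the permissive wording about past implants may simply list the timing groups in scope. Sections 3.1 and 3.2 still apply to past cases. One-year follow-up after implant and about one year of participation each (Section 5) sit badly with a wholly historical cohort. What stands is narrower: nothing makes the all-comer intent verifiable for past implants, and none of these provisions sets a look-back date.

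A reader might also infer that a closed window means missing imaging. It does not, because retrospective collection can pick up routine scans. The Protocol does not say how often those are done, so the amount of unequal ascertainment cannot be estimated from it.

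The mixed design is disclosed openly in the body, and no analysis depends on the title word. That is fair, and it makes the title a correction of wording. The entry rules are the substance.

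On the numbers, any study of 100 moves by one point per event, and the LAARGE rate covers several devices, with 25.7% of implants being Amulet. Step 6 therefore shows sensitivity and does not measure bias. The survivor calculation assumes the return-visit criterion is judged at entry; a centre judging it as of the implant date would lose fewer deaths. Appendix A lists safety outcomes at implant and pre-discharge, so peri-procedural events may be abstracted despite Section 9. The two provisions still need to agree.

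Finally, reporting by entry route could be left to an analysis plan. Eligibility, the look-back date and the start of event counting could not.

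**Conclusion.** The point holds as a design weakness that should be corrected. The full title contradicts the design stated in the body. Past implants may enter with no earliest date, no consecutive-entry rule and no limit, so selective entry is permitted, although neither intended nor shown. Scan-based outcomes in implants older than 3 months, and fully so beyond about 6.5 months, depend on routine imaging for at least one required time point. Read literally, Sections 3.1 and 9 favour survivors and can omit early events among past cases.

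The size cannot be fixed from the Protocol, because the share of past cases is not stated. The survivor effect scales directly with the share entered after a full year: none at 0%, half the deaths at 50%, all of them at 100%. These figures rest on the assumed mortality of 5% to 15% and on judging the return-visit criterion at entry. For an exploratory, descriptive study this does not invalidate the work, but it weakens the mortality, leak and thrombus estimates and the registry comparison.

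**What to change.** 1. Remove the word prospective from the full title, matching the signature page.
2. In Section 3, set one earliest implant date per centre, fixed before data abstraction. Replace the permissive wording on past cases with a consecutive list of all Amulet implants from that date. Enter every eligible case, subject to consent or ethics approval, and log the reason for each one not entered. Participation is voluntary under Section 5.1, so refusals belong in the log.
3. For retrospective cases, waive the return-visit criterion in Section 3.1, so that patients who died or cannot attend are not excluded. Amend Section 9 so that their events count from implant.
4. Reconcile the consent scope: Section 3 against Section 11 and Appendix A. Ethics approval should cover past patients who cannot consent.
5. Report primary outcomes by entry route, with leak and thrombus over the patients imaged and that number stated.

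The cost is protocol wording, an ethics submission on consent, and an implant list compiled from procedure logs at each centre. Some older cases could no longer be used to reach 100, and the prospective label is lost.

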3.1 Inclusion Criteria

- 18 year of age or older
- Documented paroxysmal, persistent, or permanent non-valvular atrial fibrillation
- At high risk of stroke or systemic embolism defined as CHA2DS2-VASc score of more than or equal to 3.
- Deemed suitable for LAA occlusion by the treating physician, who might or might not be the investigator.
- Able to comply with the required medication regimen post-device implant
- Able and willing to return for required follow-up visits and examinations

3.2 Exclusion Criteria

- With active endocarditis or other infections producing bacteremia
- Where placement of the device would interfere with any intracardiac or intravascular structures
- Reversible cause of AF (i.e. secondary to thyroid disorders, acute alcohol intoxication, trauma, recent major surgical procedures)
- Hypersensitivity to any portion of the device material or individual components of the Amulet LAA closure device
- Actively enrolled or plans to enroll in a concurrent clinical study in which the active treatment arm may confound the results of this trial
- Presence of other anatomic or comorbid conditions, or other medical, social, or psychological conditions that, in the investigator's opinion, could limit the patient's ability to participate in the clinical trial or to comply with follow up requirements, or impact the scientific soundness of the clinical trial results.

4. STUDY DESIGN

4.1 Study Description

This is a both prospective and retrospective, multicenter observational study for all patient indicated for LAAO with the Amplatzer™ Amulet™ device.

4.2 Study Outcomes

Primary outcome:

Safety:

- i. All-cause and cardiovascular mortality
- ii. Bleeding events
- iii. Pericardial effusion
- iv. Device dislocation and device related thrombus
- v. Access site complication

Efficacy:

- i. All cause and cardiovascular mortality
- ii. Ischemic stroke or transient ischemic attack
- iii. Systemic embolization
- iv. Occurrence of leak at the device supporting incomplete occlusion of the LAA.

Secondary outcomes

To compare the following with the European registries:

- i. Indication for LAA occlusion
- ii. Rate of technical and procedural success
- iii. Practice of antiplatelet and anticoagulation therapy

Exploratory outcome:

To explore on the cost effectiveness of LAAO with Amplatzer™ Amulet™ in the region.

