5.2 Criteria for Suspending or Terminating Study

Not applicable. This is an observational study and not an interventional study, the study aims to collect data of patients who had undergone the treatment, undergoing the treatment or will undergo the treatment. All the patients are managed under standard of care.

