11. INFORMED CONSENT PROCESS

Informed consents will be obtained for all prospective data collection. Consent forms describing in detail the study intervention, study procedures and risks will be given to each participant and written documentation of informed consent is required prior to starting study intervention. Participants must sign an informed consent document that has been approved by a participating centre's IEC/IRB if he/she agrees to participate in this study. Each participant should have sufficient opportunity to discuss the study and consider the information in the consent process

prior to agreeing to participate. Participants may withdraw consent at any time during the course of the trial. The informed consent form will be signed and dated by the participant and the person who conducted the informed consent discussion. Two informed consent form to be signed. One to be kept by the investigators, one to be kept by patients. No photocopy of informed consent form.

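### Retrospective entry is described by an implanted occluder in one place and more broadly elsewhere; if sites follow the narrower wording, the technical success rate compared with the European registries could be biased upward

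*Protocol*

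**What the plan says.** Protocol section 4.2 (Study Outcomes) names "Rate of technical and procedural success" as one of three secondary items to be compared with the European registries. The protocol does not define the term. The definition may stand in an analysis plan that is not shown, so its absence is not counted here as a fault.

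The protocol describes who may enter in several ways:

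- **Section 3, entry by timing:** "subjects who had their occluder implanted, been recently implanted or intended to undergo the procedure may be considered to participate in the study". The two already-treated routes name an implanted occluder. Only the third starts from intent.
- **Section 3, opening sentence:** "This is an all-comer observational study and therefore all patients indicated for LAAO with the" Amulet device are eligible. This is broader.
- **Section 4.1:** "This is a both prospective and retrospective, multicenter observational study for all patient indicated for LAAO with the" device. This is also broader.
- **Section 5.2:** "the study aims to collect data of patients who had undergone the treatment, undergoing the treatment or will undergo the treatment". A patient whose attempt ended without a device could fall under this.

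On consent, section 3 speaks generally of consent for collecting data. Section 11 says "Informed consents will be obtained for all prospective data collection", and the Appendix A row is limited in the same way ("Informed consent (For prospective data collection only").

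**The concern.** A success rate needs a denominator in which failure is possible. If a past patient is entered because an occluder is in place, and technical success means that an occluder was placed, that patient's result is known before enrolment. Patients enrolled before the procedure can still fail. Pooling the two groups removes a share of the failures and raises the rate.

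The error would run in one direction, in favour of the device. It would not shrink with more patients, and a pooled confidence interval would not show it. An analysis plan can split results by entry route, but it cannot restore past failed attempts that no site entered. For that reason the entry wording belongs in the protocol.

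The other two registry comparisons, indication and antithrombotic practice, are not affected by this mechanism.

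**Working it through.** **Step 1. Is there a figure to reproduce?** No. The 100 patients in section 8.2 are a recruitment estimate without a success rate, error level or power. The protocol gives no retrospective share and no technical success rate for the registries. The 98.4% in section 1 is complete closure, which is a different quantity.

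**Step 2. Does the wording exclude past failures?** Read literally, the timing sentence in section 3 has no route for a past attempt that ended without a device. Two other places lean the same way: the Protocol Summary counts follow-up from the implant, and one inclusion criterion in section 3.1 concerns medication after it. Against this, sections 3.1 and 3.2 do not require an implanted device, and the wording of sections 4.1 and 5.2 allows past failures. Two centres could follow the protocol in good faith and build different denominators.

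**Step 3. Bias under the narrower reading.** Let f be the retrospective share, s the true success rate per attempt, and m = 100(1 − f) the number of subjects who can fail.

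- Pooled rate = (1 − f)s + f
- Bias = f(1 − s)
- Example: s = 0.95, f = 0.50 gives 0.5 × 0.95 + 0.5 = 0.975, a bias of 2.5 points. Expected failures fall from 5 to 2.5 per 100.

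All values of f and s below are assumptions.

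| s | f | Pooled rate | Bias (points) | Coverage of s by pooled 95% Wilson interval, n = 100 |
|---|---|---|---|---|
| 95% | 25% | 96.25% | 1.25 | 97.5% |
| 95% | 50% | 97.5% | 2.5 | 92.3% |
| 95% | 75% | 98.75% | 3.75 | 72.3% |
| 98% | 25% | 98.5% | 0.5 | 98.3% |
| 98% | 50% | 99.0% | 1.0 | 99.7% |
| 98% | 75% | 99.5% | 1.5 | 100% |

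Coverage is exact binomial: (100 − m) fixed successes plus a Binomial(m, s) count. With no retrospective entrants it is 96.6% at s = 95%. A material loss appears in one of the six cells.

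**Step 4. Which remedy reduces the error?** The root mean squared error (RMSE, in points) was compared for three approaches:

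- Pooled under the narrower reading: 100 × √(bias² + m·s(1 − s)/100²), with bias as a proportion
- Prospective subjects only: 100 × √(s(1 − s)/m)
- All attempts entered: 100 × √(s(1 − s)/100)

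| s | f | Pooled | Prospective only | All attempts entered |
|---|---|---|---|---|
| 95% | 25% | 2.26 | 2.52 | 2.18 |
| 95% | 50% | 2.94 | 3.08 | 2.18 |
| 95% | 75% | 3.91 | 4.36 | 2.18 |
| 98% | 25% | 1.31 | 1.62 | 1.40 |
| 98% | 50% | 1.41 | 1.98 | 1.40 |
| 98% | 75% | 1.66 | 2.80 | 1.40 |

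Restricting to prospective subjects removes the bias but has a larger RMSE than pooling in all six cells. Its approximate 95% half-width at s = 95%, 1.96 × √(s(1 − s)/m), is 4.9, 6.0 and 8.5 points with 75, 50 and 25 subjects, against 4.3 with all 100. Entering every attempt removes the bias and keeps n at 100.

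**The case against.** The strongest reply is that the timing sentence in section 3 only explains that past, recent and future patients may all be considered, and is not a filter on the result of the procedure. The sentence that governs eligibility covers everyone with an indication, and the formal criteria contain no implanted-device requirement. On that reading past failures are already admitted and the bias is nil. This is a fair reading and it stands as a possibility. It does not remove the ambiguity, because the only sentence that tells a site how to recognise a past patient names an implanted device.

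A second reply is that denominators and analysis sets belong in the analysis plan. That holds for defining success and for a prospective-only analysis. It does not hold for past failures that were never entered.

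A third is that the size rests on assumed values. This stands. Section 1 offers one weak clue: 163 described as 25.7% implies a base of about 634 (163/0.257), against 641 in the LAARGE registry. If 634 were the implanted patients, success there would be about 98.9%, a range in which the bias is small. That is inference only.

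A reader might go further and infer that technical success is, as a matter of fact, an entry condition for part of this cohort, or that the registry comparison is invalid. The documents do not support this. The broader wording allows past failures, the meaning of technical success is not given, pooling is not stated, and nothing shows how the registries count failed attempts. A reader might also extend the point to procedural success. That is not established: the term is undefined, and a patient with a device in place can still have had a procedural complication.

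**Conclusion.** The point holds as a conditional one, of minor severity. The protocol describes retrospective entry more narrowly in one sentence of section 3 than in the rest of section 3 and in sections 4.1 and 5.2. The technical success rate is biased upward by f(1 − s) if three conditions hold: sites follow the narrower wording, technical success means device implantation, and entry routes are pooled. For the registry comparison to be biased to that extent, the registries must also count failed attempts.

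Over an assumed retrospective share of 25 to 75%, the bias is 0.5 to 1.5 points at a true rate of 98% and 1.25 to 3.75 points at 95%. It is zero if all past attempts are entered, and small if failures are rare or the retrospective share is low. It touches one descriptive secondary outcome; the argument does not bear on the primary safety and efficacy outcomes.

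**What to change.** Reword the timing sentence in section 3 to agree with sections 4.1 and 5.2, so that retrospective entry covers all consecutive past Amulet implant attempts at each centre, including those that ended without a device. State that all attempts form the denominator of technical success. Report the rate by entry route with 95% confidence intervals. Keep the prospective-only rate as a sensitivity result and not as the replacement estimate, given its larger RMSE.

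The cost is modest. Each centre must list its past attempts. The consent wording for retrospective data must be reconciled, because section 3 is general while section 11 and Appendix A limit consent to prospective data. The reported rate may turn out slightly less favourable.
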